5.6. Accountability for Study Drug

The investigator (or designee, eg, study center pharmacist) is responsible for ensuring adequate accountability of all used and unused study drug. This includes acknowledgment of receipt of each shipment of study drug (quantity and condition). Each study site must keep accountability records that capture:

- The date received and quantity of study drug kits.
- The date, participant number, and the study drug kit number dispensed.
- The date, quantity of used and unused study drug returned, along with the initials of the person recording the information.

5.6.1. Study Drug Return or Disposal for Lenacapavir and Placebo to Match Lenacapavir Tablets

Gilead recommends that used and unused study drug supplies be destroyed at the site. If the site has an appropriate standard operating procedure (SOP) for drug destruction as determined by Gilead, the site may destroy used (empty or partially empty) and unused study drug supplies in accordance with that site's approved SOP. A copy of the site's approved SOP will be obtained for electronic Trial Master File. If study drug is destroyed on site, the investigator must maintain accurate records for all study drugs destroyed. Records must show the identification and quantity of each unit destroyed, the method of destruction, and the person who disposed of the study drug. Upon study completion, copies of the study drug accountability records must be filed at the site. Another copy will be returned to Gilead.

If the site does not have an appropriate SOP for drug destruction, used and unused study drug supplies are to be sent to the designated disposal facility for destruction. The study monitor will provide instructions for return.

The study monitor will review study drug supplies and associated records at periodic intervals.

For both disposal options listed above, the study monitor must first perform drug accountability during an on-site monitoring visit, unless otherwise agreed with the sponsor and documented.

6. STUDY PROCEDURES

The study procedures to be conducted for each participant enrolled in the study are presented in tabular form in [Appendix 2](#), and described in the text that follows.

The investigator must document any deviation from the protocol procedures and notify the Gilead or CRO.

6.1. Participant Enrollment and Treatment Assignment

Entry into screening does not guarantee enrollment into the study. In order to manage the total study enrollment, Gilead, at its sole discretion, may suspend screening and/or enrollment at any site or study-wide at any time.

6.2. Pretreatment Assessments

6.2.1. Screening Assessments

Participants will be screened within 42 days prior to enrollment in the study. Each participant will be assigned a unique screening number using the IWRS.

The following will be performed and documented at screening:

- Obtain written informed consent—related events, available historical genotype/phenotype reports, available HIV-1 treatment history, substance (ie, illicit drug) use and prior medications within 30 days of the screening visit.
- Complete physical examination (urogenital/anorectal examinations will be performed at the discretion of the investigator) including, vital signs, body weight, and height.
- 12-lead ECG performed supine.
- Obtain blood and urine samples as noted in [Section 6.5](#).
- Record any SAEs and all AEs related to protocol-mandated procedures occurring after signing of the consent form.
- Select an OBR based on the screening and/or available historical HIV resistance reports.
 - Availability of selected OBR must be confirmed prior to randomization/enrollment and participant must be able to initiate OBR as specified in the protocol.
- Return to the clinic between 14 and 30 days after the screening visit, for a Cohort Selection visit. HIV-1 RNA results from this visit will be used to determine whether eligible participants will participate in Cohort 1 or Cohort 2.
 - Once enrollment in Cohort 1 is complete, Cohort Selection visit will not be required.

Participants meeting all the inclusion criteria and none of the exclusion criteria will return to the clinic within 42 days after screening for a Day 1 visit. Participants will be instructed to continue their failing regimen.

Participants not meeting one or more inclusion criteria and/or meeting one or more exclusion criteria may be rescreened on a case-by-case basis upon written approval from Gilead medical monitor or study director.

From the time of obtaining informed consent through the first administration of study drug, record all SAEs, as well as any AEs related to protocol-mandated procedures on the AEs eCRF. All other untoward medical occurrences observed during the screening period, including exacerbation or changes in medical history are to be considered medical history. See Section 7 Adverse Events and Toxicity Management for additional details.

6.3. Treatment Assessments

6.3.1. Functional Monotherapy Period and Oral Lead-in Period Assessments

Cohort 1: Eligible participants will be randomized in Cohort 1 if they have a $< 0.5 \log_{10}$ HIV-1 RNA decline compared to the screening visit and HIV-1 RNA ≥ 400 copies/mL at the Cohort Selection visit. Approximately 3 days prior to the Day 1 visit, investigator or designee may randomize the participant to receive oral LEN or placebo to match LEN and obtain a participant number using IWRS. Cohort 1 participants will have a Functional Monotherapy Period. Participants will continue to receive their failing regimen during this period.

Cohort 2: Eligible participants will be enrolled in Cohort 2 if Cohort 1 is fully enrolled or if they do not meet the criteria for randomization in Cohort 1 (eg, they had a $\geq 0.5 \log_{10}$ HIV-1 RNA decline compared to the screening visit and/or HIV-1 RNA < 400 copies/mL at the Cohort Selection visit). Approximately 3 days prior to the Day 1 visit, investigator or designee may enroll the participant using IWRS and obtain a participant number. Cohort 2 participants will have an oral lead-in period and will initiate an OBR (as prescribed by the investigator) on Day 1.

All participants will complete the following study visits: Days 1, 2, 5 (± 1 day) (Day 5 visit is optional, but every effort should be made to complete this visit) and 8. The following procedures are to be completed at the Day 1 visit, prior to study drug dosing and at Days 2, 5 (± 1 day) and 8, unless otherwise noted.

- Prior to completion of other study procedures, participants ≥ 18 years of age at the Day 1 visit will read the Patient Reported Outcomes, if available, by himself/herself and provide answers directly onto the questionnaires.
 - Symptoms Distress Module, Short Form Health Survey (SF-36), EQ-5D-5L at Day 1.
- Review of AEs and changes in concomitant medications.
- Complete physical examination (urogenital/anorectal examinations will be performed at the discretion of the investigator) (Day 1 only) or symptom-directed physical examination as needed at Days 2 and 8.

- Vital signs and body weight (except at Day 5).
- Obtain blood and urine samples collection as noted in Section 6.5.
- After completion of study assessments, Cohort 1 participants will receive oral LEN 600 mg, 600 mg, and 300 mg or placebo to match on Days 1, 2, and 8 respectively.
 - Cohort 1 participants will continue on their failing regimen.
- After completion of study assessments, Cohort 2 participants will receive oral LEN 600 mg, 600 mg, and 300 mg on Days 1, 2, and 8 respectively.
 - Cohort 2 participants will initiate an OBR (as prescribed by the investigator) at Day 1. Participants will take last dose of their failing regimen prior to Day 1 visit.
- All study drug dosing will occur at the study center without regard to food.
- Document study drug administration.
- After each participant completes the Functional Monotherapy Period, their treatment assignment will be unblinded.

6.3.2. Maintenance Period Assessments

All participants will complete a Maintenance Period. The Gilead medical monitor should be consulted prior to administration of SC LEN in the Maintenance Period if a participant was not administered all doses of oral LEN during the Functional Monotherapy Period in Cohort 1 or the Oral Lead-in Period in Cohort 2.

All participants will complete the following study visits: Day 1 SC (14 days after the first dose of oral LEN), Weeks 4, 10, 16, 22, 26, 36, and 52. At the Week 52 visit, participants will be given an option to continue receive SC LEN 927 mg and to complete study visits at Weeks 62, 78, 88, 104, 114, 130 and will continue to alternate between every 10 weeks and every 16 weeks.

At Week 156 and thereafter, upon regulatory and/or IRB/IEC approval of the protocol and when participants have provided written informed consent of the most current IRB-approved consent form, participants will continue to receive study drug every 26 weeks, and continue to attend visits every 26 weeks (± 2 weeks). Participants will receive SC LEN every 6 months (26 weeks) ± 2 weeks from the last injection starting at the Week 156 visit, while continuing their OBR, until the product becomes accessible to participants through an access program, is commercially available, or until Gilead elects to discontinue the study in the country.

Study visits Week X are identified by the number of weeks that have elapsed since the Day 1 SC visit when LEN is first administered by injection and excludes Oral Bridging Periods.

Cohort 1B participants will complete the following study visits prior to receiving SC LEN: Days 15, 16, 19 (± 1) (Day 19 visit is optional, but every effort should be made to complete this visit), and 22. They will receive oral LEN 600 mg, 600 mg, and 300 mg on Days 15, 16, and 22, respectively.

Participants may require oral bridging if an SC injection of LEN cannot be administered within the protocol visit window. In case of Oral Bridging initiation, participants will receive oral LEN as specified in Section 5.4 and complete Oral Bridging visits. An Oral Bridging visit should be completed every 10 to 12 weeks. Additional visits during the oral weekly administration may be conducted per investigator's discretion. Upon restarting LEN SC injection, an SC dosing visit will restart (eg, Week 52, Week 78), with follow-up visits in between occurring as specified in this protocol.

Week 4 visit through Week 52 visit are to be completed within ± 2 days of the protocol-specified visit date based on the Day 1 SC visit. Following the completion of Week 52 visit, visits are to be completed within ± 6 days of the protocol-specified visit date. Each SC LEN dosing should occur within 26 and 28 weeks of the previous SC LEN dosing.

The following procedures are to be completed at all visits unless otherwise noted.

- Participants ≥ 18 years of age at the Day 1 visit will read the Patient Reported Outcomes, if available, by himself/herself and provide answers directly onto the questionnaires.
 - Participants will complete Symptoms Distress Module, Short Form Health Survey (SF-36), EQ-5D-5L at Weeks 4, 16, 26, and 52 (these questionnaires should be completed prior to the completion of other study procedures).
 - Participants to complete the Numeric Pain Rating Scale at Day 1 SC, Weeks 26 and 52 (this questionnaire should be completed after the participant received their SC LEN injections).
- Review of AEs and changes in concomitant medications.
- Complete physical examination (Day 15 [Cohort 1B only], Day 1 SC, Weeks 26 and 52) (urogenital/anorectal examinations will be performed at the discretion of the investigator) or symptom-directed physical examination as needed (except at Days 5 and 19).
- Obtain vital signs and body weight (except at Days 5 and 19).
- Obtain blood and urine samples as noted in Section 6.5.
- Cohort 1 participants who received oral LEN during randomized phase will receive SC LEN 927 mg and initiate their OBR on Day 1 SC visit (14 days after the first dose of oral LEN) (**Cohort 1A**). Participants will continue to receive SC LEN 927 mg every 6 months (26 weeks) ± 2 weeks from last injection thereafter while continuing their OBR.

- Cohort 1 participants who received placebo to match LEN during randomized phase will receive oral LEN 600 mg and initiate their OBR on the Day 15 visit after completion of Day 15 assessments (**Cohort 1B**). Participants will receive oral LEN 600 mg and 300 mg on Days 16 and 22 respectively while continuing their OBR.
- Cohort 1B participants will receive SC LEN 927 mg at the Day 1 SC visit while continuing on their OBR (14 days after the first dose of oral LEN). Participants will continue to receive SC LEN 927 mg every 6 months (26 weeks) \pm 2 weeks from last injection thereafter while continuing their OBR.
- Cohort 2 participants will receive SC LEN 927 mg at the Day 1 SC visit while continuing on their OBR (14 days after the first dose of oral LEN). Participants will continue to receive SC LEN 927 mg every 6 months (26 weeks) \pm 2 weeks from last injection thereafter while continuing their OBR.
- SC study drug administration will occur at the study center without regard to food.
- Provide ISR assessment worksheet and instruct the participants to measure and report ISRs following the administration of the SC injections.
- For all participants on oral weekly bridging, the first dose of oral LEN will be administered at the study center without regard to food and up to 2 bottles will be provided to the participant with instructions to take the remaining doses at home once a week (1 \times 300 mg LEN) without regard to food on the same day of the week that the first dose was given.
- Document study drug administration.
- Document study drug accountability.
- Participants who meet the criteria for virologic failure will be managed according to the Management of Virologic Failure Section 6.7.

The Week 156 visit and visits every 26 weeks thereafter are to be completed within \pm 2 weeks of the protocol-specified visit date. Each SC LEN dosing should occur within 26 weeks \pm 2 weeks of the previous SC LEN dosing.

The following procedures are to be completed at all visits unless otherwise noted.

- Review of AEs and changes in concomitant medications.
- Symptom-directed physical examination.
- Obtain vital signs and body weight.
- Obtain blood and urine samples as noted in Section 6.5.
- SC study drug administration will occur at the study center without regard to food.

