1.2.2.1. GS-US-200-5709

Study GS-US-200-5709 was a Phase 1, open-label, multicohort, multidose oral and/or subcutaneous (SC) LEN study to evaluate the safety, tolerability, and PK of multiple-dose oral and SC LEN in healthy participants. A total of 76 participants were enrolled in 3 cohorts as follows:

- Cohort 1: oral LEN 600 mg (2 × 300-mg tablets) given on Days 1 and 2, oral LEN 300 mg (1 × 300-mg tablet) on Day 8, and SC LEN 927 mg on Day 15 (2 × 1.5 mL of LEN injection, 309 mg/mL sodium salt). All doses were administered under fed conditions.
- Cohort 2: SC LEN 927 mg (2 × 1.5 mL of LEN injection, 309 mg/mL sodium salt) and oral LEN 600 mg (2 × 300-mg tablets) administered on Day 1 followed by oral LEN 600 mg (2 × 300-mg tablets) on Day 2, was evaluated. All doses were administered under fed conditions.
- Cohort 3: Oral LEN 600 mg (2 × 300-mg tablets) was given twice daily for 10 days with last dose given in the morning on Day 11.

The conclusions from this study were as follows:

- Lenacapavir administered as an SC injection or as tablets was generally safe and well tolerated. All injection site reactions (ISRs) were Grade 1 or 2 in severity.
- For Cohorts 1 and 2, mean LEN concentrations and their lower bound 90% CIs exceeded inhibitory quotient (IQ) 1 (protein-adjusted effective concentration at 95% [paEC₉₅] from MT-4 cells; 3.87 ng/mL) within a few hours of dosing on Day 1, achieved IQ4 (15.5 ng/mL) within 2 hours after dosing on Day 2, and maintained above IQ4 through the desired dosing interval of 26 weeks after the SC dose.
- The C_{max} was achieved approximately 12 weeks and 10 weeks (median T_{max}) after the SC dose for Cohorts 1 and 2, respectively. Mean LEN C_{max} (%CV) was 58.7 ng/mL (58.1%) and 62.7 ng/mL (39.2%) for Cohorts 1 and 2, respectively.
- For the dosing interval of 26 weeks, mean estimate of AUC_{Days 1-197} for Cohort 1 and AUC_{Days 1-183} for Cohort 2 were 166,024 ng•h/mL and 159,097 ng•h/mL, respectively.

- In Cohort 3, LEN exhibited significant accumulation over the course of 10 days of twice daily oral dosing; C_{\max} and AUC_{0-12h} were 53-fold and 72-fold higher, respectively, on Day 11 compared with Day 1.

For further information, refer to the current edition of the IB.

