### 3.8. Analysis Visit Windows

#### 3.8.1. Definition of Key Dates and Study Day

**First Dose Date** for All LEN Analysis is defined as the earliest dose date of either blinded or open-label oral LEN, as recorded on the Study Drug Administration eCRF form.

**Last Dose Date** for All LEN Analysis is defined for participants who prematurely discontinue study drug in any phase (ie, main phase or extension phase) of the study or who complete study drug as the latest dose date of either blinded or open-label oral LEN or SC LEN.

**First Dose Date** for the study is defined as the day when the first dose of blinded study drug (LEN or Placebo) or open-label oral LEN was taken, as recorded on the Study Drug Administration eCRF form.

**Last Dose Date** for the study is defined for participants who prematurely discontinue study drug in any phase of the study or who complete study drug as the latest dose date of any study drug including blinded study drug, open-label oral LEN, and SC LEN.

**First Dose Date of Oral Bridging** is defined for participants who received oral bridging of LEN as the earliest dose date of oral bridging of LEN, as recorded on the Study Drug Administration - Oral Bridging eCRF form.

**Last Dose Date of Oral Bridging** is defined for participants who received oral bridging of LEN, as the latest dose date of oral bridging of LEN before the First Dose Date of Resumed SC Injection, as recorded on the Study Drug Administration - Oral Bridging eCRF form.

**First Dose Date of Resumed SC Injection** is defined for participants who received oral bridging of LEN and resumed the SC injection, as the earliest dose date of SC LEN following the lifting of the Clinical Hold on SC LEN, as recorded on the Study Drug Administration – SC eCRF form.

**Last Study Date** is defined as the latest date of non-missing clinic visits and/or laboratory visits, and/or AE onset and end dates without any imputation, including the 30, 90, and 180-day follow-up visit dates for participants who prematurely discontinue or complete the study.

**Study Day** will be calculated from the First Dose Date, as defined separately above for All LEN Analysis and for the study, and will be derived as follows:

- For postdose study days: Assessment Date – First Dose Date + 1
- For study days prior to the first dose: Assessment Date – First Dose Date

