### **4.2. Study Drug Administration and Adherence**

Study drug administration and study drug dispensing information will be collected in the Study Drug Administration and Study Drug Accountability eCRFs. Number of participants receiving oral lead-in LEN and SC LEN at each protocol specified visit (Day 1, Day 2, Day 8, Day 15, Day 16, and Day 22 for oral LEN and Day 1 SC, Week 26, Week 52, Week 78, Week 104, and etc. for SC LEN) will be summarized. Number of participants receiving oral reload before the first SC injection due to missed scheduled oral dosing, and number of participants receiving oral bridging after the first SC injection will also be provided.

Study drug administration and dispensing information including lot number and kit ID (if applicable) will be listed.

The adherence to SC LEN will be assessed by adherence to the projected injection interval, which is 26 weeks (182 days) between 2 adjacent injection visits. The number of days from the projected injection visit date will be calculated for each injection visit (excluding the 1st injection visit) as the injection visit date minus the previous injection visit date minus 182 days minus oral bridging period (ie, First Dose Date of Resumed SC Injection - First Dose Date of Oral Bridging) if any occurred between these 2 adjacent injection visits. The number of days from the projected injection visit date will be classified into the following categories:

- < - 14 days
- -14 to -8 days
- -7 to -3 days
- ± 2 days
- 3 to 7 days
- 8 to 14 days
- > 14 days

The number and percentage of participants in each category will be summarized by cohort and treatment group and overall for the injection visits of interest.

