#### **6.2.1. US FDA-defined Snapshot Algorithm**

The analysis window at Week 104 is defined as from Study Day 688 to Study Day 778, inclusive, where Study Day is calculated from the first dose of oral LEN. Participants who have missing HIV-1 RNA at Week 104 and have completed the study before reaching the upper limit of the analysis window for Week 104 will be excluded. All HIV-1 RNA data collected on-treatment will be used in the snapshot algorithm.

HIV-1 RNA on-SC-LEN-treatment is defined as HIV-1 RNA collected up to 28 weeks from the last SC LEN, and on or prior to the first dose of oral bridging of LEN or up to 28 weeks from any resumed SC LEN after oral bridging for participants who received oral bridging of LEN.

HIV-1 RNA on-oral-LEN-treatment is defined as HIV-1 RNA collected after the First Dose Date of Oral Bridging or oral reload after the first SC LEN, and up to 7 days from the Last Dose Date of Oral Bridging for participants who discontinued from the oral bridging of LEN, or up to minimal (Last Dose Date of Oral Bridging +7, First Dose Date of Resumed SC Injection) for participants who resumed SC LEN.

For the snapshot algorithm, HIV-1 RNA on-SC-LEN-treatment will be used. If there is no such result, HIV-1 RNA on-oral-LEN-treatment will be used.

Virologic outcome will be defined as the following categories:

- HIV-1 RNA < 50 copies/mL: this includes participants who have the last available on-treatment HIV-1 RNA < 50 copies/mL in the Week 104 analysis window
- HIV-1 RNA  $\geq$  50 copies/mL: this includes participants
  - Who have the last available on-treatment HIV-1 RNA  $\geq$  50 copies/mL in the Week 104 analysis window, or
  - Who do not have on-treatment HIV-1 RNA data in the Week 104 analysis window and
    - Who discontinue study drug prior to or in the Week 104 analysis window due to lack of efficacy, or
    - Who discontinue study drug prior to or in the Week 104 analysis window due to reasons other than AE, death, or lack of efficacy and have the last available on-treatment HIV-1 RNA  $\geq$  50 copies/mL
- No Virologic Data in the Week 104 analysis window: this includes participants who do not have on-treatment HIV-1 RNA data in the Week 104 analysis window because of the following:
  - Discontinuation of study drug prior to or in the Week 104 analysis window due to AE or death (regardless of whether the last available on-treatment HIV-1 RNA < 50 copies/mL or not) or,

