  - Discontinuation of study drug prior to or in the Week 104 analysis window due to reasons other than AE, death, or lack of efficacy and the last available on-treatment HIV-1 RNA < 50 copies/mL or,
  - Missing data during the window but on study drug.

The number and percentage of participants with HIV-1 RNA < 50 copies/mL, HIV-1 RNA  $\geq$  50 copies/mL, and reasons for no virologic data at Week 104 will be summarized. The 95% CI for the percentage of participants with HIV-1 RNA < 50 copies/mL will be constructed using the Exact method.

The proportion of participants with HIV-1 RNA < 200 copies/mL at Week 104, and the proportion of participants with HIV-1 RNA < 50 copies/mL and < 200 copies/mL at Week 156 will also be summarized in the same manner using the US FDA-defined snapshot algorithm. The analysis window at Week 104 is defined as from Study Day 779 to Study Day 869, inclusive.

The flowchart of the US FDA-defined snapshot algorithm is provided in Section 12 ([Appendix 1](#)).

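### The Week 104 and Week 156 snapshot windows run on calendar days while visits are numbered net of oral bridging, so a completed shift of about 36–56 days can leave an on-drug participant with no scheduled HIV-1 RNA in the window

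*Protocol*

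**What the plan says.** **Visit clock.** Protocol 6.3.2 identifies Week X by the time elapsed "since the Day 1 SC visit when LEN is first administered by injection and excludes Oral Bridging Periods". After bridging, the schedule resumes where it stopped: "Upon restarting LEN SC injection, an SC dosing visit will restart (eg, Week 52, Week 78".

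**Analysis clock.** SAP 3.8.1 derives Study Day with no bridging term: "For postdose study days: Assessment Date – First Dose Date + 1". SAP 6.2.1 takes the initial oral LEN dose as its origin: "The analysis window at Week 104 is defined as from Study Day 688 to Study Day 778, inclusive, where Study Day is calculated from" that dose. Protocol 8.5.2 and SAP Table 3-1 give the same Week 104 range, and 1052–1142 for Week 156. (The closing text of SAP 6.2.1, where a Week 156 range would be expected, gives Days 779–869 labelled Week 104. That is the Week 114 row of Table 3-1 and needs correcting separately.)

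**Scoring.** One reason listed in SAP 6.2.1 for the *No Virologic Data* category is "Missing data during the window but on study drug". The section's one added exclusion is for participants with missing RNA who completed the study before the window's upper limit.

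**Where bridging is allowed for.** The injection-adherence calculation in SAP 4.2 subtracts it: "minus oral bridging period (ie, First Dose Date of Resumed SC Injection - First Dose Date of Oral Bridging". SAP 6.2.1 also adapts the on-treatment definition, using on-oral results when there is no on-SC result. The windows themselves are not adapted.

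**The concern.** A completed bridging period moves every later scheduled visit by its length, but the windows stay where they are. In this part of the schedule the two visits before and at the target week are 16 weeks (112 days) apart, while the window is 91 days long. Some shifts therefore place one visit before the window and the next after it. A participant who attended every scheduled visit, remained on LEN and was suppressed would stay in the denominator without entering the numerator. The cause would be the interaction of two rules, not missed attendance or virologic failure. Week 104 and Week 156 are the secondary endpoints that this SAP was written to analyse.

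**Working it through.** **Inputs.** Day 1 SC is Study Day 15 (SAP Table 3-1). Visits after Week 52 alternate at 10 and 16 weeks, with a tolerance of ±6 days; the Week 156 visit has ±2 weeks (Protocol 6.3.2). Oral Bridging visits are 10 to 12 weeks apart. Enrolment is 72 (Protocol 1.2.2.2).

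**1. Reproduce the plan's figures.** Nominal day = 15 + 7 × week.

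- Week 78: 561; Week 88: 631; Week 104: 743; Week 114: 813.
- Week 140: 995; Week 156: 1107; Week 166: 1177.

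The window bounds are the midpoints between neighbouring nominal days: (631 + 743)/2 = 687 and (743 + 813)/2 = 778 give 688–778; (995 + 1107)/2 = 1051 and (1107 + 1177)/2 = 1142 give 1052–1142. Both match Table 3-1.

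**2. Shift the visits.** Let S be the total shift: bridging plus any delay before it started. Assume that bridging ended before the window opened.

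- The Week 104 visit is past the window when 743 + S > 778, so S ≥ 36.
- The Week 88 visit is still before it when 631 + S < 688, so S ≤ 56.
- For S = 36–56 days no scheduled visit is inside. At S = 36 the visits fall on Days 667 and 779.
- Week 156 gives the same limits at nominal days: 1107 + S > 1142 and 995 + S < 1052.

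This is about 5 to 8 weeks, less than the 12 consecutive weeks beyond which Protocol 5.4 asks that the sponsor be contacted.

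**3. Add the visit tolerances.**

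| Window | Empty for certain | Empty possible |
|---|---|---|
| Week 104 (±6 days at both visits) | S − 6 ≥ 36 and S + 6 ≤ 56: 42–50 | S + 6 ≥ 36 and S − 6 ≤ 56: 30–62 |
| Week 156 (±6 days at Week 140, ±14 at Week 156) | S − 14 ≥ 36 and S + 6 ≤ 56: 50 only | S + 14 ≥ 36 and S − 6 ≤ 56: 22–62 |

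**4. Other shifts, at nominal days.**

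- S = 0–35: the planned 26-week visit is inside. No harm.
- S = 57–147: the last scheduled reading inside is the Week 88 (or Week 140) visit, because 631 + 57 = 688 and 631 + 147 = 778. It is 10 weeks after an injection, not 26.
- S = 148–217: the last reading is again a 26-week or resumption visit.
- If bridging took place early enough, the pattern repeats after 182 days, with empty windows at 218–238.
- Bridging that starts at the Week 104 or Week 156 visit, or long bridging that overlaps the window, leaves a sample inside.

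**5. Effect on the rate.** One empty window costs 1/72 = 1.4 percentage points. Purely as illustration, 2 would cost 2.8, 5 would cost 6.9 and 10 would cost 13.9. These counts are assumed.

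**The case against.** The calendar window is the protocol's own. Protocol 8.5.2 fixes both ranges, and the endpoint is worded as Weeks 104 and 156 from the first SC dose, which supports elapsed time. A reader might infer that the SAP therefore reports something other than the protocol's endpoint. The documents do not support that, and the calendar result should stay. Nor is the subtraction in SAP 4.2 proof of an error: it measures the gap between two injections, where bridging has to come out.

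Bridging was also considered. SAP 6.2.1 has an on-oral fallback, reasons for missing data are tabulated, and a Missing = Excluded analysis by visit is planned. This stands only in part. The fallback finds nothing when bridging ended before the window. The listed reason does not separate a shifted schedule from a missed visit. Missing = Excluded is a different analysis and removes every missing value, whatever its cause. An unscheduled sample could fill the window, but the plan does not call for one.

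A reader might also infer that the 10-week reading flatters the result, since LEN C_max "was achieved approximately 12 weeks and 10 weeks" after the SC dose. That figure is from healthy participants. The same section reports mean concentrations above IQ4 through 26 weeks, and Protocol 1.5 regards IQ4 as giving near-maximal activity. No bias in the proportion < 50 copies/mL is shown.

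**Conclusion.** The point holds as a structural gap in the analysis rules. At nominal visit days, a completed shift of 36–56 days leaves the Week 104 or Week 156 window without a scheduled HIV-1 RNA. Tolerances change the two weeks differently, so Week 156 should not be treated as identical: an empty window is certain for shifts of 42–50 days at Week 104, but only at about 50 days for Week 156.

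The cost is about 1.4 points per affected participant on each rate, if the denominator is 72. The actual denominator may be smaller because of the completed-study exclusion. The total is unknown. SAP 2.1.4 describes an oral bridging analysis already conducted, and SAP 3.8.1 dates resumption "as the earliest dose date of SC LEN following the lifting of the Clinical Hold on SC LEN". So bridging happened, and a hold could give several participants similar shifts, but neither numbers nor durations are stated.

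Two stronger readings fail. Affected participants are not scored as ≥ 50 copies/mL; they lack virologic data. And not every bridged participant is affected: shifts up to 35 days do no harm at nominal days. The endpoints are descriptive and secondary, and the primary endpoint is untouched.

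**What to change.** Keep the Protocol 8.5.2 calendar-window snapshot. In SAP 6.2.1 add a pre-specified bridging-adjusted snapshot at Weeks 104 and 156 that uses the protocol-labelled visit, and record it in SAP 6.5:

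- For assessments after resumption, subtract accumulated bridging days (the SAP 4.2 term) from Study Day before assigning windows. Define the term for each bridging period, because SAP 3.8.1 ties the resumption date to the clinical hold while Protocol 5.4 allows bridging for any reason.
- Assign samples taken during a completed bridging period to that period. Otherwise the adjusted clock runs backwards. With bridging from Day 561 to Day 711, a sample on Day 701 would sit in the Week 104 window, while the later Week 78 and Week 88 visits are adjusted to Days 561 and 631.
- Use the same adjusted day in the rules on not having reached, or having completed the study before, the upper limit (SAP 6.2.1 and Appendix 3 item 8).
- Report how many participants have an empty calendar window because of bridging.

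**Check.** Subtracting the whole shift returns the visits to Days 743 and 1107 for every shift tested (0–364 days). The SAP 4.2 term leaves in any delay before bridging began. A delay of 14 days is still absorbed: 743 + 14 + 6 = 763 ≤ 778, and 1107 + 14 + 14 = 1135 ≤ 1142.

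**Cost.** Extra SAP text and programming, a later data cut for bridged participants, and possibly more exclusions of those who complete the study before the shifted upper limit.
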